**Prolonged Prone Positioning for COVID-19-induced Acute
Respiratory Distress Syndrome (ARDS): A Pilot Study**

NCT 04581811

Date of Protocol: 10/1/2020

Prolonged Prone Positioning for COVID-induced ARDS

Primary Investigator: [name]
Address: [name]
[name]
Mailbox: [name]

[name], K, [name], [name], [name], [name], [name]

Introduction:

The Novel Coronavirus has resulted in a pandemic of patients with respiratory failure, the most ill subset of which are experiencing Acute Respiratory Distress Syndrome (ARDS). Few therapies have demonstrated efficacy in treating this novel illness.[1-4] Prone ventilation is one of the few interventions known to decrease mortality in ARDS.[5] Prone positioning has become ubiquitous with the COVID-19 pandemic, expanding to even include non-intubated patients and now getting attention in the lay press.[6-10]

A major limitation to the most impactful implementation of prone positioning is that the ideal duration of prone ventilation is unknown. The landmark study on prone positioning demonstrating a mortality benefit used a 16 hour prone session followed by a supine period.[5] The rationale behind using a 16h strategy was not based on physiologic or outcomes data. There is retrospective, observational data suggesting that improvements in oxygenation may increase with duration of prone positioning extending beyond 16 hours to at least 24 hours. [11, 12] Further, decreasing the number of times position is changed decreases nursing burden and may decrease the rate of inadvertent line or tube displacement, the most feared complication of proning. Other potential risks associated with the act of changing position include transient changes in hemodynamics and oxygenation which would also be expected to occur less frequently with prolonged proning.

Early in the pandemic, we noticed that some patients experienced severe desaturations when returned to the supine position. This led to an alteration in clinical practice where patients were left in the prone position for longer than the standard 16 hours, some up to 72 hours. Given the recent emphasis on prone positioning, the variation in clinical practice and the protracted course of mechanical ventilation experienced by patients with COVID-ARDS, we felt there was equipoise to evaluate prolonged prone positioning in a prospective fashion.

This study was designed as a pilot safety and feasibility study.

Methods

Patient & Public Involvement:

Patient and family information sheets were developed and submitted to the UAB IRB for approval. Upon enrollment, the patient information sheets were given the bedside nurse to be placed with patient belongings. Study authors will disseminate study findings online and via social media in lay person-appropriate language.

Study Design:

The Prolonged Prone Positioning for COVID-19-induced ARDS is a pragmatic, randomized, single-center, parallel-arm study. Patients undergoing prone positioning for COVID-induced ARDS will be randomized to receive either traditional (16 hour) or prolonged (24 hour) prone ventilation sessions. This

study was approved under waiver of informed consent by the UAB IRB in keeping with the federal Office for Human Research Protections guidelines (45 CFR 46.116).

Study Sites:

The Prolonged Prone Positioning for COVID-19-induced ARDS study is being conducted across intensive care units at the University of Alabama at Birmingham Hospital.

Population

This trial includes adults (≥ 18 years old) located across any ICU at UAB Hospital who are endotracheally intubated in whom the treating physician plans to implement prone positioning imminently. Patients must have a P:F ratio of ≤ 150 on at least 60% FiO₂ and at least 10cm H₂O of PEEP after ventilator optimization to be included. The primary cause of respiratory failure must be thought to be most likely due to COVID-19 ARDS (e.g. not a patient with a massive aspiration event or an acute heart failure exacerbation who is incidentally found to have COVID-19). This trial excludes patients with pre-existing treatment limitation (i.e. DNR order), prisoners, pregnant females, patients who have been on mechanical ventilation for ≥ 48 hours at the time of screening and any patient in whom there is a contraindication to prone positioning (e.g. open abdomen, severe hemodynamic instability). Finally, patients may be excluded for physician discretion.

Randomization & Treatment Allocation:

Patients were randomized using even numbered blocks in a 1:1 fashion. Treatment allocation was sealed in opaque, sequentially numbered envelopes. After screening was performed and eligibility determined, a member of the treatment team opened the sealed envelope and informed the bedside nurse of the treatment allocation. A sign was then placed on the door of the patient with treatment allocation to inform all staff of the patient's involvement in the study and the treatment allocation.

Study Intervention:

Patients in a UAB ICU who were intubated and in whom the treating physician planned on initiating prone positioning for COVID-induced ARDS were screened for inclusion and exclusion criteria. Inclusion and exclusion criteria were documented on the screening form, and baseline ABG and ventilator settings were documented. Following enrollment, an opaque envelope was opened revealing treatment allocation. The bedside nurse was provided with a form stating the treatment allocation.

If patients are randomized to the traditional proning arm, the patient will be placed in the prone position for 16 hours. Following the 16-hour prone session, the patient will be returned to the supine position. After 4 to 6 hours in the supine position, an ABG is to be drawn. If the P:F ratio is < 150 while on 10 cmH₂O of PEEP and 60% FiO₂, the patient will be returned to the prone position. If the patient is not immediately eligible for reproning at this time but subsequently has a P:F ratio of < 150 on requisite ventilator settings, they will be repositioned to the prone position. This process will be continued as long as the patient was eligible. The patient will remain in the same treatment allocation arm.

If randomized to the prolonged proning arm, the patient will be placed in the prone position for 24 hours. Following the 24-hour prone session, the patient will be returned to the supine position. After 4 to 6 hours in the supine position, an ABG will be drawn. If the P:F ratio is < 150 while on 10 cmH₂O of PEEP and 60% FiO₂, the patient will be returned to the prone position. If the patient is not immediately eligible for reproning at this time but subsequently has a P:F ratio of < 150 on requisite ventilator settings, they will be repositioned to the prone position. This process will be continued as long as the patient was eligible. The patient will remain in the same treatment allocation arm.

All other care will be directed by the treating team and/or unit/hospital protocols.

Data Collection:

Data collection will be performed through a combination of data collection forms completed by the treatment team and EMR abstraction.

Sample Size Calculation:

This study was designed as a pilot study to evaluate the safety and feasibility. We anticipated an 8h change in duration prone and a standard deviation of 10h along resulting in an initial sample size of 52 patients.

DSMB & Interim Analysis:

Given the pace of enrollment and relatively small sample size, no interim analysis will be performed. This study will be stopped early for poor recruitment if enrollment drops below 8 patients enrolled on a rolling 4-week period.

Statistical Analysis:

Stata 16.1 (StataCorp, College Station, TX) will be used for all statistical analysis. Continuous variables will be presented as means with standard deviation or median with interquartile range. Comparisons will be made with the student's t-test or Mann-Whitney U test, as appropriate. Categorical variables will be reported as frequencies and proportions. Categorical variables will be compared using the Chi² test. A p-value of 0.05 will be considered significant.

Handling of Missing Data:

We have planned for no missing data in our power calculation.

Specific Aim 1:

Determine if the protocolized use of prolonged prone positioning results in an increased duration prone in the first 96 hours after proning

Hypothesis:

Patients randomized to receive prolonged prone positioning will spend more hours prone.

Specific Aim 2:

Compare the effect of traditional prone-positioning to prolonged prone-positioning on physiologic data, specifically improvements in P:F ratio and pulmonary mechanics.

Hypothesis: Patients who undergo prolonged prone positioning will have improved physiologic characteristics on day 4 when compared to those in the standard prone duration arm, as measured by P:F ratio and driving pressure.

Research Plan Overview: We propose a pragmatic, open-label, randomized trial of 52 patients in a 1:1 ratio to traditional proning strategy vs. prolonged proning.

Plan for Consent: We will perform this study under waiver of informed consent based on HHS Code of Federal Regulation (45 CFR 46).

IRB Category: Expedited review – Approved

Expected Duration of Study: We expect this study to last approximately 5-6 months at a rate of 8-10 patients enrolled per month.

Expected Results: We expect to find that our study is feasible. We expect to observe a trend towards improved pulmonary mechanics in patients undergoing prolonged prone positioning.

Potential Significance: If successful, this data could provide justification for a large-scale, multicenter randomized controlled trial. The researchers involved in this study have existing relationships with a large, national group capable of performing a multicenter study[13-19]. Ultimately, this research could result in decreased duration of mechanical ventilation and therefore mortality with subsequent increased hospital capacity and cost savings. The potential impact of this study is massive.

Potential Pitfalls: The most obvious potential pitfall for this study is sample size. This is unlikely to be a major issue for multiple reasons: 1) Our UAB MICU has treated a large number of COVID-ARDS patients, many of whom have received prone ventilation 2) Our screening strategy will default to inclusion in the study – given the potential for decreased positioning changes, this will have enthusiastic nursing support to encourage enrollment

Funding: This is an unfunded study. A study coordinator and statistical support has been provided by the UAB Lung Health Center *gratis*.

References:

1. Cao, B., et al., *A Trial of Lopinavir-Ritonavir in Adults Hospitalized with Severe Covid-19*. N Engl J Med, 2020. **382**(19): p. 1787-1799.
2. Shah, S., et al., *A systematic review of the prophylactic role of chloroquine and hydroxychloroquine in coronavirus disease-19 (COVID-19)*. Int J Rheum Dis, 2020. **23**(5): p. 613-619.
3. Cohen, M.S., *Hydroxychloroquine for the Prevention of Covid-19 - Searching for Evidence*. N Engl J Med, 2020.
4. Valk, S.J., et al., *Convalescent plasma or hyperimmune immunoglobulin for people with COVID-19: a rapid review*. Cochrane Database Syst Rev, 2020. **5**: p. Cd013600.
5. Guérin, C., et al., *Prone Positioning in Severe Acute Respiratory Distress Syndrome*. New England Journal of Medicine, 2013. **368**(23): p. 2159-2168.
6. Elharrar, X., et al., *Use of Prone Positioning in Nonintubated Patients With COVID-19 and Hypoxemic Acute Respiratory Failure*. JAMA, 2020. **323**(22): p. 2336-2338.
7. Xu, Q., et al., *Early awake prone position combined with high-flow nasal oxygen therapy in severe COVID-19: a case series*. Crit Care, 2020. **24**(1): p. 250.

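### Does N = 52 fail because its 8 h difference and 10 h SD are not tied to Aim 1's 96-hour total of prone hours?

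*Combined protocol and SAP*

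**What the plan says.** The Sample Size Calculation section presents the study as a pilot of safety and feasibility and gives one sentence of derivation: "We anticipated an 8h change in duration prone and a standard deviation of 10h along resulting in an initial sample size of 52 patients". The significance level is in the Statistical Analysis section ("A p-value of 0.05 will be considered significant"), which allows either Student's t-test or the Mann-Whitney U test. The 1:1 allocation of 52 patients is in the Research Plan Overview. Handling of Missing Data adds: "We have planned for no missing data in our power calculation". No power, sidedness or source for the SD appears anywhere.

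Specific Aim 1 is worded: "Determine if the protocolized use of prolonged prone positioning results in an increased duration prone in the first 96 hours after proning".

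Under Study Intervention, sessions last 16 h or 24 h. In the 16-hour arm, "After 4 to 6 hours in the supine position, an ABG is to be drawn", and the patient is turned prone again if P:F is below 150 on the stated ventilator settings. The 24-hour arm has the same rule. Later re-proning is also provided for ("If the patient is not immediately eligible for reproning at this time but subsequently has a P:F ratio" below the threshold), and "This process will be continued as long as the patient was eligible".

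**The concern.** The 8 h equals 24 − 16, the contrast for one session, while Aim 1 counts hours over four days. Two patients in the same arm whose session counts differ by one can differ by 16 or 24 h. An SD of 10 h for the 96-hour total then looks small unless nearly everyone has the same number of sessions. If the true SD is nearer 20 h and the gap does not grow to match, 52 patients give far less than 80% power.

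Interpretation would suffer too. A null result on total hours could mean that the longer sessions were not delivered. It could also mean that they were delivered but the 24 h arm met the re-proning trigger less often. The second is plausible, because Aim 2 hypothesises better P:F in the prolonged arm and P:F is the trigger. A pilot meant to support a larger trial would want to tell these apart.

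**Working it through.** **1. Reproducing 52.** Inputs from the protocol: difference 8 h, SD 10 h, 1:1 allocation, alpha 0.05, no missing data. Assumed, because not stated: two-sided test, 80% power.

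- Normal approximation: n per arm = 2 × (1.96 + 0.84)² × 10² / 8² = 24.5, rounded up to 25, so 50 in total.
- t-test: with 26 per arm, the noncentrality is 0.8 × √(26/2) = 2.88 on 50 degrees of freedom, and power is 80.7%. With 25 per arm it is 79.1%. So 26 per arm, 52 in total, is an exact match.
- One-sided 0.05 at 26 per arm gives 88.5%, and one-sided 90% by normal approximation needs 54. The figure 52 does not by itself prove which convention was used, but two-sided 80% fits exactly.

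**2. The 96-hour gap implied by the schedule.** Sessions of exactly 16 or 24 h, supine interval of 4, 5 or 6 h, cut off at 96 h:

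| Sessions | 16 h arm | 24 h arm | Gap |
|---|---|---|---|
| 1 each | 16 h | 24 h | 8 h |
| 2 each | 32 h | 48 h | 16 h |
| 3 each | 48 h | 72 h | 24 h |
| 4 each | 64 h | 84 / 81 / 78 h | 20 / 17 / 14 h |
| Uninterrupted (5 vs 4 started) | 80 / 76 / 72 h | 84 / 81 / 78 h | 4 / 5 / 6 h |

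Example for uninterrupted cycling with a 5 h interval: 4 × 16 + 12 = 76 h against 3 × 24 + 9 = 81 h. The planned 8 h lies inside the range of 4 to 24 h.

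**3. Gap and SD can move together.** A 16 h gap with an SD of 20 h has the same standardised effect, 16/20 = 8/10 = 0.8, and so needs the same 52. An 8 h gap with an SD of 20 h would give 29% power.

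**4. Power for the 96-hour total under assumed re-proning.** The documents give no re-proning rate. Let q be an assumed probability of re-proning at each supine check, the same in both arms, with supine time uniform on 4 to 6 h and 26 per arm, two-sided 0.05. By simulation, with no later return:

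| q | SD | t-test | Mann-Whitney |
|---|---|---|---|
| 0.1 | 7 h | 99% | about 100% |
| 0.3 | 14 h | 79% | 95–97% |
| 0.5 | 20 h | 57–58% | about 71% |
| 0.7 | 24 h | 43–44% | 57% |
| 0.9 | 20 h | 35% | 95–96% |
| 0.98 | 10 h | 59–60% | about 100% |
| 1.0 | 1 h | about 100% | about 100% |

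Now suppose that a quarter or half of those not re-proned at the check return later, after a further mean of 24 h. For q from 0.3 to 0.9 the SD is then 16 to 23 h and t-test power 38 to 67%. Mann-Whitney gives roughly 52 to 64% at q = 0.5 to 0.7 and 97% at q = 0.9.

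The two tests part at q = 0.9 because most patients cycle without a break and their totals cluster tightly, while a few early stoppers inflate the SD. Ranks are little affected by those few.

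**5. Unequal re-proning.** With q = 0.7 in the 16 h arm and 0.5 in the 24 h arm and no later return, the gap is about 0 h although every session is delivered in full. These rates are also assumed.

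**6. Precision.** The 95% CI half-width for the difference is 2.009 × SD × √(2/26), which is 5.6 h at SD 10 h and 11.1 h at SD 20 h.

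**The case for a change.** The strongest case for a change is that 52 was derived from a between-arm comparison and will be read against a 0.05 threshold, so calling the study a pilot does not excuse unstated inputs. At middling re-proning rates (q of 0.5 to 0.7) power falls below 80% by either test: about 43 to 58% by t-test and about 52 to 72% by Mann-Whitney. The Potential Pitfalls section names sample size as the main risk but answers only on recruitment. Stating the assumptions and tabulating sessions per patient would cost almost nothing.

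Much of this stands. The omissions are real, and the mid-range shortfall would be real if re-proning ran at those rates. But every rate behind it is an assumption, and the same model gives ample power when re-proning is rare or nearly universal. Limits and worst cases quoted for the t-test alone, such as 35% at q = 0.9, do not represent a plan that equally allows Mann-Whitney.

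The link to Aim 1 is looser than it should be but not absent. The sample-size sentence and Aim 1 both speak of duration prone, and no other outcome does.

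The worry about interpretation is weaker. Aim 1 asks whether the protocolised strategy, re-proning rule included, leads to more hours prone. Total hours answers that question directly. Nothing in the plan treats a non-significant total as failed delivery.

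**Conclusion.** No change to the plan is needed. The sample size section is terse: it omits power, sidedness, window and the basis of the SD. Even so, 52 follows exactly from its inputs under the usual convention (two-sided 0.05, 80.7% power), and 8 h lies within the 4 to 24 h that the protocol's schedule can produce over 96 hours. The plan claims no power that its design can be shown to miss. Whether 8 h and 10 h suit the 96-hour total is unsupported rather than disproved, since the answer depends on re-proning rates found nowhere in the documents.

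Restating the assumptions would alter neither N, the outcome nor the data collected. Confidence intervals, session counts and first-session hours are descriptive summaries of times that must be recorded anyway to compute hours prone, and an analyst can be expected to produce them. This is a gap in reported detail, and Aim 1's answer about total hours does not depend on filling it. The conclusion would differ if the documents gave a re-proning rate in the middle range, or made a decision on the larger trial hinge on significance for total hours. They do neither.

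### The mandatory recruitment stopping rule (fewer than 8 in any rolling 4 weeks) sits inside the planned accrual range, so a trial recruiting to plan would probably be closed

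*Combined protocol and SAP*

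**What the plan says.** The DSMB & Interim Analysis section rules out an interim analysis and then sets one stopping rule: "This study will be stopped early for poor recruitment if enrollment drops below 8 patients enrolled on a rolling 4-week period". It gives no first checking date, checking frequency, number of consecutive low windows, or room for judgement.

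The Expected Duration of Study section gives the accrual plan: "We expect this study to last approximately 5-6 months at a rate of 8-10 patients enrolled per month". The Research Plan Overview sets the total: "We propose a pragmatic, open-label, randomized trial of 52 patients in a 1:1 ratio to traditional proning strategy vs. prolonged proning".

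The Potential Pitfalls section raises the size of the trial ("The most obvious potential pitfall for this study is sample size") and then explains why this is unlikely to matter much. It does not mention the stopping rule. The Expected Results section adds: "We expect to find that our study is feasible".

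**The concern.** A futility rule for recruitment should separate a trial that is failing to recruit from one that is recruiting as intended. Here the floor is about equal to the planned rate. The rule is worded as an obligation and applies to every rolling window, so one ordinary slow month is enough to close the trial.

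The Introduction and the Sample Size Calculation section describe a pilot of safety and feasibility. Closing it for poor recruitment while it was on plan would misrepresent feasibility. It would also leave too few patients for Specific Aim 1, the comparison of hours prone. The rule does not look at outcomes, so it does not bias the comparison between arms.

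**Working it through.** **Inputs from the documents.** Floor of 8 per rolling 4 weeks (DSMB & Interim Analysis); 8 to 10 per month for about 5 to 6 months (Expected Duration of Study); 52 patients, 1:1 (Research Plan Overview); difference 8 h and SD 10 h (Sample Size Calculation); significance level 0.05 (Statistical Analysis). Assumed, because not stated: two-sided test, 80% power, a month of 365.25/12 = 30.44 days.

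**The plan's own figures.** Standardised effect 8/10 = 0.8. The two-sample t-test needs 25.5 per arm, so 26 per arm and 52 in total, with 80.7% power. The sample size reproduces. Duration is 52/10 = 5.2 to 52/8 = 6.5 months, close to the stated 5 to 6.

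**Step 1: put rule and plan on the same scale.** Rate per 28 days = monthly rate × 28/30.44.

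- 8 per month: 7.36
- 9 per month: 8.28
- 10 per month: 9.20
- Rates implied by 52 patients in 6 or 5 months: 52/6 = 8.67 gives 7.97; 52/5 = 10.4 gives 9.57

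Break-even is 8 × 30.44/28 = 8.70 per month. Below that, the average window breaches the rule. At the top of the plan the margin is 9.20 − 8 = 1.20 or 9.57 − 8 = 1.57 patients. This step needs no accrual model.

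**Step 2: one window.** If counts are Poisson, P(7 or fewer) is 54.5%, 41.5% and 30.1% at 8, 9 and 10 per month. At 10 per month the SD is √9.20 ≈ 3.0, so the margin is about 0.4 SD.

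**Step 3: the whole trial.** Patient arrivals were simulated up to patient 52, counting the preceding 28 days from day 28 onward (20,000 runs per setting). The wording could also mean that a count of 8 must be reached before it can drop, so that reading is included. Separate 4-week blocks are more lenient than the rolling window in the text.

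| Poisson accrual, calendar month | 8/month | 9/month | 10/month |
|---|---|---|---|
| Daily checks | 99.9% | 99% | 97% |
| Weekly checks | 99.7% | 98% | 94% |
| Separate 4-week blocks | 98% | 93% | 82% |
| Daily, 8 first reached | 99.7% | 99% | 96% |
| Weekly, 8 first reached | 99% | 96% | 90% |
| Blocks, 8 first reached | 91% | 84% | 71% |

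At the duration-implied 8.67 and 10.4 per month, weekly checks give 99% and 90%.

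**Step 4: milder assumptions.**

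- Month means 4 weeks, 10 per month, Poisson: about 92% (daily), 85% (weekly), 67–68% (blocks), 57% (blocks, 8 first reached).
- Accrual much more regular than Poisson (gamma gaps, coefficient of variation 0.5), calendar month, weekly checks: about 99.9%, 97% and 75–79% at 8, 9 and 10 per month.
- Regular accrual, 10 per 4 weeks: about 47% (weekly), 27% (blocks), and about 20% (blocks, 8 first reached).
- Perfectly even accrual: at 8 per calendar month about 64% of windows hold 7 patients; at 9 to 10 per month none breaches the rule.

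**Step 5: what is left at stopping (Poisson, calendar month).** Median enrolment at 8, 9 and 10 per month is 7, 9 and 12 with daily checks. If 8 must first be reached it is 13, 14 and 16 (daily) or 17, 19 and 20 (weekly). With separate blocks and 8 first reached it is about 25 to 27. Power for the planned effect (noncentral t, effect 0.8, two-sided 0.05) is 24% at 12 patients, 32% at 16, 40% at 20 and about 50% at 26, against 81% at 52.

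**The case against.** Four points can be made for the plan.

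- **Month may mean 4 weeks.** The plan is then 8 to 10 per window, and the rule says to stop below the lowest planned rate, which is coherent. This stands as a possible reading. But the floor then equals the bottom of the plan, and Poisson accrual at the top rate still triggers it in about 85% of trials with weekly checks.
- **The size depends on unstated assumptions.** It does: results run from 99.9% to about 20%, and to zero for perfectly even accrual at 9 to 10 per month. At 8 per calendar month the breach is mainly a mismatch of units, not chance. However, the low figures need several favourable assumptions at once, including separate blocks, which contradict the rolling window. Nothing in the documents supports near-even arrival of ventilated COVID-19 patients at one hospital.
- **The harm is operational.** The documents set no recruitment criterion for feasibility and do not say that closure would mean the approach is infeasible. Neither the sample size calculation nor the validity of the comparison is touched. This is right and limits the seriousness. Closing at a fraction of 52 would still defeat the pilot's purpose.
- **Investigators would use judgement.** The text gives them none. If judgement is intended, the protocol should say so.

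**Conclusion.** The concern holds. The rule and the accrual plan conflict on simple arithmetic: 8 lies within 7.4 to 9.2 per 28 days, or on the lower edge of 8 to 10 if a month means 4 weeks. No other section relieves this. Read as written, with Poisson accrual and daily or weekly rolling checks, the rule closes 90% or more of trials recruiting at 8 to 10 per calendar month, usually with no more than 20 patients enrolled.

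The direction is secure. The exact percentages rest on the Poisson assumption, the calendar month and a first check at day 28. Pandemic surges would probably make counts more variable than Poisson; more regular accrual lowers the risk, mainly at the top of the planned range.

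**What to change.** Reconcile the rule with the accrual plan. Either make it a non-binding trigger for a feasibility review by the investigators, or set the threshold clearly below planned accrual over a longer window. In both cases define the window in days and state when checks start and how often they occur.

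Example wording: *Enrollment will be checked weekly from week 8; fewer than 6 patients in the preceding 8 weeks triggers a feasibility review, not automatic closure.*

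Two illustrative thresholds, simulated with Poisson accrual and weekly checks from day 56 (10,000 runs per rate):

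| True rate per month | Under 6 in 8 weeks | Under 8 in 8 weeks |
|---|---|---|
| 10 (on plan) | 0.3% | 2.5% |
| 9 (on plan) | 1% | 8% |
| 8 (on plan) | 5% | 20% |
| 7 | 15% | 46% |
| 6 | 38% | 76% |
| 5 | 75% | 96% |

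The looser threshold flags about 97% of trials at 4 per month and nearly all at 3. The documents give no acceptable false-alarm rate, so the investigators should state one and choose the threshold from it. If the trigger is non-binding, a false alarm costs only a review, which favours the stricter threshold.

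The cost is one or two sentences in the protocol, a first check at week 8, and some moderately slow trials missed. With the looser threshold, unflagged trials at 5 and 6 per month take a median of about 9 and 8 months, against the planned 5 to 6.

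### Aim 2 compares day-4 P:F ratio by an unadjusted two-sample test, although baseline P:F is known for every patient before allocation; prespecifying baseline adjustment would be a small, cheap improvement

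*Combined protocol and SAP*

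**What the plan says.** - **Analysis method.** Statistical Analysis gives one general rule for continuous variables, the "t-test or Mann-Whitney U test, as appropriate". No regression, analysis of covariance or other baseline adjustment appears anywhere in the document.
- **Outcome.** The aim sentence of Specific Aim 2 refers to physiologic data, "specifically improvements in P:F ratio and pulmonary mechanics". Its hypothesis is that the prolonged arm "will have improved physiologic characteristics on day 4 when compared to those in the standard prone duration arm", judged by P:F ratio and driving pressure. The hypothesis reads most naturally as a comparison of day-4 levels; the aim sentence leaves a change from baseline open.
- **Baseline value.** The Population section makes oxygenation an entry criterion ("Patients must have a P:F ratio of" 150 or less, on minimum oxygen and PEEP settings). Study Intervention says that "baseline ABG and ventilator settings were documented".
- **Order of events.** Randomization & Treatment Allocation states: "After screening was performed and eligibility determined, a member of the treatment team opened the sealed envelope". Baseline P:F therefore precedes knowledge of the arm.
- **Purpose and size.** Sample Size Calculation says: "This study was designed as a pilot study to evaluate the safety and feasibility". The 52 patients are derived from hours prone (Aim 1). No power, SD or correlation is given for Aim 2, and Expected Results anticipates only a trend in pulmonary mechanics.

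**The concern.** A baseline measurement of the same quantity as the outcome, taken before allocation in every patient, is usually the most useful covariate a small trial has. If it predicts the day-4 value, a model containing it gives a narrower interval for the arm effect than a test of day-4 levels alone. If the aim is instead read as change from baseline, baseline P:F is used, but with its slope forced to 1, which is generally less efficient than estimating the slope.

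What is at stake is the precision of the Aim 2 estimate. Potential Significance says the data could help justify a multicenter trial, so that estimate may be carried forward. A second, smaller gain is that the adjusted model removes the choice between level and change on whichever scale is fixed.

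**Working it through.** **1. The plan's own figure.** Inputs from Sample Size Calculation: difference 8 h, SD 10 h, so d = 8/10 = 0.8. Power and sidedness are not stated; I assume 80% and a two-sided 5% level. The normal formula gives n = 2(1.960 + 0.842)²/0.8² = 24.5, so 25 per arm (50 in total). The exact t-test gives 79.1% power with 25 per arm and 80.7% with 26 per arm, so 26 per arm reproduces 52. This concerns Aim 1 only.

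**2. Assumptions for Aim 2.** None is in the documents: a true day-4 difference of 0.6 SD, normal data, a two-sided 5% level, 26 evaluable per arm (52/2, nobody missing), and a baseline to day-4 correlation ρ varied from 0 to 0.5.

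**3. Unadjusted day-4 level.** Noncentrality = 0.6 × √(26/2) = 2.163 on 50 df; power 0.5643.

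**4. Adjusted for baseline.** The variance is multiplied by f = (1 − ρ²)(1 + 1/48), where the second term is the cost of estimating the slope (N − 4 = 48). Noncentrality = 2.163/√f on 49 df. Example, ρ = 0.3: f = 0.91 × 1.0208 = 0.929; 2.163/√0.929 = 2.245; power 0.5950.

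| ρ | f | Adjusted power (level: 0.5643) | CI width relative to unadjusted |
|---|---|---|---|
| 0 | 1.021 | 0.5553 | 1.01 |
| 0.2 | 0.980 | 0.5724 | 0.99 |
| 0.3 | 0.929 | 0.5950 | 0.96 |
| 0.4 | 0.857 | 0.6294 | 0.93 |
| 0.5 | 0.766 | 0.6786 | 0.88 |

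Break-even is at ρ ≈ 0.146. The greatest loss is 56.4% − 55.5% = 0.9 points.

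**5. Fewer evaluable patients.** With 20 per arm (factor 1 + 1/36, 37 df), the level test has power 0.4560. Adjusted power is 0.4456, 0.4605, 0.4805 and 0.5576 at ρ = 0, 0.2, 0.3 and 0.5. Break-even rises to 0.169 and the greatest loss to 1.0 point.

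**6. Change score.** Let k = baseline SD / day-4 SD. The variance relative to the day-4 level is 1 + k² − 2ρk = (1 − ρ²) + (k − ρ)². The first term is the adjusted model's variance without its estimation penalty, so the change score can win only when k is close to ρ, and then only by about that penalty.

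| ρ | Change, k = 1 | Change, k = 0.75 | Change, k = 0.5 | Adjusted |
|---|---|---|---|---|
| 0.2 | 0.3889 | 0.4715 | 0.5441 | 0.5724 |
| 0.3 | 0.4339 | 0.5206 | 0.5858 | 0.5950 |
| 0.4 | 0.4908 | 0.5803 | 0.6336 | 0.6294 |
| 0.5 | 0.5643 | 0.6531 | 0.6879 | 0.6786 |

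**7. Effect of the entry limit on ρ.** A cap at 150 narrows the baseline range. For a normal baseline truncated above, with SD ratio s, ρ′ = ρs/√(ρ²s² + 1 − ρ²). If 150 lies at the 25th, 50th or 75th percentile of an unselected population (assumed), s = 0.492, 0.603 or 0.731. An unselected correlation of 0.5 becomes 0.27 to 0.39, 0.4 becomes 0.21 to 0.30, and 0.3 becomes 0.15 to 0.22.

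**8. Level or change in the adjusted model.** Subtracting baseline from the outcome lowers the baseline coefficient by exactly 1 and leaves the arm coefficient, its standard error and its p-value unchanged. This holds within one scale: a log model covers log level and log change, not raw change.

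**The case against.** The strongest objection is that this is close to a matter of preference. The trial is a pilot, Aim 2 carries no power claim, and at correlations of 0.2 to 0.3 the gain is only 0.8 to 3.1 points. The effect size, the correlation, the SD ratio and the position of the cap are all assumed. After truncation, an unselected correlation of 0.3 sits between break-even and a very small gain. An entry cap with no cap on day 4 also makes a smaller baseline SD plausible, and with k = 0.5 a change score is within about 1 point of adjustment at ρ = 0.3 and slightly ahead at 0.4 and 0.5. All of this stands, and it limits the weight of the point. It does not remove it, because the covariate is already collected, the worst case is small, and the alternative wording of the outcome is settled at the same time.

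It also stands that patients with no day-4 P:F may matter more. Handling of Missing Data says only that none was planned for in the power calculation. That is a separate question, which baseline adjustment does not answer.

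Three stronger readings are tempting and unsupported:
- A reader might infer that chance baseline imbalance makes the planned tests wrong. Under randomization either test, chosen in advance, keeps its 5% level on average.
- A reader might infer that the plan ignores baseline altogether. That fails if the aim sentence means change from baseline.
- A reader might infer that level and change would both be tested and the better result reported. Nothing in the documents says so.

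**Conclusion.** The point holds as a low-weight improvement to consider. The plan names only unadjusted two-sample tests for Aim 2, while a pre-allocation baseline P:F exists for every enrolled patient. There is no error and no threat to validity, and Aim 1 and the sample size of 52 are unaffected.

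Under the stated assumptions the benefit over the day-4 level test ranges from a loss of 0.9 points at zero correlation to a gain of 11.4 points (56.4% to 67.9%, from unrounded values) at 0.5. How much is realized depends on a correlation that the documents do not supply and that the entry cap probably lowers. Against a change score the advantage is larger when the two SDs are similar and disappears when the baseline SD is about half the day-4 SD. Confidence in the facts is high; confidence in the size of the gain is moderate at best.

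**What to change.** Add two or three sentences to Statistical Analysis:
- Define day-4 P:F as the Aim 2 outcome, analysed by a linear model on arm plus baseline P:F.
- Fix the scale, raw or log, in advance rather than choosing it from the data. Report the adjusted difference (raw) or ratio (log) with its 95% CI.
- Adjust day-4 driving pressure for its baseline value only if baseline driving pressure can be confirmed as available from the "data collection forms completed by the treatment team and EMR abstraction". Recorded ventilator settings alone do not show that a plateau pressure was measured. Otherwise keep the planned unadjusted comparison for it.
- State separately how patients without a day-4 value are handled.

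The model is one command in the software already named. For P:F it needs no new data and no change to the sample size. The statistical cost is one degree of freedom, with the small worst-case power loss shown in steps 4 and 5 of the working, somewhat larger as evaluable numbers fall.
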